Endpoints	
PRIMARY ENDPOINT
 
The primary safety endpoint will be the number and proportion of participants, per dose group and randomized allocation, with at least one of the following adverse events between Day 0 (Visit 2) and Day 28 (Visit 8)
 
 • Cough and spasmodic cough of grade 2 or higher. • Other respiratory tract AE related or possibly related to vaccination of grade 3 or higher. • Any other AE related or possibly related to vaccination of grade 3 or higher 
SECONDARY SAFETY ENDPOINTS
 
Number and proportion of participants, per dose group and randomized allocation, with:
 
 • at least one episode of cough or spasmodic cough, described by grade, between Day 4 and Day 28 • at least one solicited or unsolicited AEFI from respiratory tract between Day 0 and Day 28 • at least one AEFI with difficulties in breathing (asthma, spasmodic cough, pneumonia) between Day 0 and Day 28 • at least one other AEFI from the respiratory tract between Day 0 and Day 28 • at least one episode of cough, described by grade, between Day 0 and Day 28 • at least one episode of spasmodic cough, described by grade, between Day 0 and Day 28 • at least one solicited systemic AEFI between Day 0 and Day 28 (fever, headache, tiredness) • at least one unsolicited AEFI between Day 0 and Day 28 • at least one SAE related or possibly related to vaccination declared between D28 and the end of the trial 
Adverse events following immunization (AEFI) should be reported at study visits during the first 28 days of the concerned subject.
 
Serious adverse events (SAE) should be reported immediately but no later than 24 hours after detection. AEFI which lead to difficulties in breathing (asthma, spasmodic cough, pneumonia) will be considered as serious and reported to the Data Safety Monitoring Board (DSMB) and the sponsor.
 
Other secondary endpoints
 
COLONIZATION OF THE BPZE1 STRAIN IN THE NASOPHARYNGEAL MUCOSA
 
Per dose group and randomized allocation:
 
 • Number and proportion of participants who have been colonized by the modified B. pertussis strain BPZE1 at each post-vaccination visit • Number of visits during which bacteria are detected • Magnitude of bacterial colonization (number of cfu) per post-vaccination visit 
IMMUNOGENICITY
 
Per dose group and randomized allocation:
 
 • IgG and IgA antibodies against PT, FHA, PRN, and fimbriae 2/3 in serum at visits 2, 4, 6, 7, 8 and 9 
 • Geometric mean levels • Number and proportion of participants with positive responses, defined by at least 100% increase from pre- to post-vaccination, to at least 4 times MLD (minimum level of detection) after vaccination 
Sera will be tested blindly for pertussis specific IgG antibodies in batch for each group. Antibody levels to PT, FHA, PRN, and fimbriae 2/3 will be expressed in IU/mL calibrated against reference antisera from the National Institute for Biological Standards and Controls.

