XIII. Recording and reporting of Adverse Events Following Immunization

XIII.1. DEFINITIONS

Adverse Event Following Immunization

In this study AEFI are defined according to the current definition generally used in vaccine pharmacovigilance (Report of CIOMS/WHO Working Group on vaccine pharmacovigilance 2012) as: *"any untoward medical occurrence which follows immunization and which does not necessarily have a causal relationship with the usage of the vaccine. The adverse event may be any unfavourable or unintended sign, abnormal laboratory finding, symptom or disease."*

Serious Adverse Event

An AEFI is considered as serious adverse event (SAE) or a serious adverse reaction (SAR)

- results in death;
- is life-threatening (means that the subject was at immediate risk of death at the time of the event; it does not refer to an event which hypothetically might have caused death if it were more severe);
- requires hospitalization or prolongation of existing hospitalization;
- results in persistent or significant disability or incapacity;
- is a congenital anomaly or birth defect;
- is an "important medical event" (medical events, based upon appropriate medical judgment, which may jeopardize the subject or may require medical or surgical intervention to prevent one of the above characteristics/consequences);

Examples: allergic bronchospasm requiring intensive treatment at an emergency room or at home, blood dyscrasias, convulsions that do not result in inpatient hospitalization, suspected transmission of an infectious agent via a medicinal product...

Is a special interest Adverse Event:

- clinical pertussis in a colonized individual if wild type *B. pertussis* is not detected by culture or PCR.

EXCEPTIONS: SAE not requiring immediate reporting to the sponsor

- Medical or surgical procedures (e.g.: surgery, endoscopy, tooth extraction, transfusion); only the condition that leads to the procedure should be notified if the condition is referring to a seriousness criteria described above.
- Pre-existing diseases or present conditions or detected prior to start of study drug administration that do not worsen.
- Situations where an untoward medical occurrence has not occurred (e.g.: hospitalization for elective surgery if known prior to start study, social and/or convenience admissions, pre-specified study hospitalizations for observation).

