- Outpatient care; the volunteer has been formally admitted to a hospital for medical reasons with no seriousness criteria (described above) and does not require overnight hospitalization.

Adverse Reaction

AR are all untoward and unintended responses to an IMP related to any dose administered. All adverse events judged by either the reporting investigator or the sponsor as having a reasonable causal relationship to a medicinal product qualify as AR. This definition covers also medication errors and uses outside what is foreseen in the protocol, including misuse and abuse of the product. The expression reasonable causal relationship means to convey in general that there is evidence or argument to suggest a causal relationship.

An adverse event is considered an AR if the investigator or sponsor indicates that the adverse event is possibly, probably or definitely related to the study vaccine or placebo (relationship to an excipient).

In addition, any SAE assessed by the investigator as possibly, probably or definitely related to a protocol-specified intervention is considered a serious adverse reaction (SAR).

Suspected Unexpected Serious Adverse Reaction (SUSAR)

An unexpected serious adverse reaction is a serious adverse reaction of a nature, outcome or severity of which is not consistent with the investigational study vaccines Investigator's Brochure.

New fact

A new fact is defined as any safety data that could modify significantly the evaluation of the benefit/risk ratio of the clinical trial.

A new fact is defined as any new events related to the conduct of a trial or the investigational vaccine likely to affect the safety of subjects.

Examples: a serious adverse event which could be associated with the trial procedures and which could modify the conduct of the trial, a significant hazard to the subject population such as lack of efficacy of an investigational vaccine used for the treatment of a life-threatening disease, recommendations of the DSMB where relevant for the safety of subjects.

Relationship of an Adverse Event to the Study Vaccine

The relationship of an adverse event to the study vaccine has to be determined by the PI or delegate as follows:

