2.1.2. SECONDARY SAFETY ENDPOINT

The second safety endpoint will be the number and proportion of participants per dose group and randomized allocation, with:

- at least one episode of cough or spasmodic cough, described by grade, between Day 4 and Day 28
- at least one solicited or unsolicited AEFI from respiratory tract between Day 0 and Day 28
- at least one AEFI with difficulties in breathing (asthma, spasmodic cough, pneumonia) between Day 0 and Day 28
- at least one other AEFI from the respiratory tract between Day 0 and Day 28
- at least one episode of cough, described by grade, between Day 0 and Day 28
- at least one episode of spasmodic cough, described by grade, between Day 0 and Day 28
- at least one solicited systemic AEFI between Day 0 and Day 28 (fever, headache, tiredness)
- at least one unsolicited AEFI between Day 0 and Day 28

AEFI should be reported at study visits during the first 28 days of the concerned subject.

SAE should be reported immediately but no later than 24 hours after detection. AEFI which lead to difficulties in breathing (asthma, spasmodic cough, pneumonia) will be considered as serious and reported to the DSMB and the sponsor.

- **Analysis strategy**

Analytical strategies will be the same as the primary endpoint analytical strategies.

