2.1.3. OTHER SECONDARY ENDPOINT

1) Colonization of the BPZE1 strain in the nasopharyngeal mucosa:

Per dose, group and randomized allocation:

- Number and proportion of participants who have been colonized by the modified *B. pertussis* strain BPZE1 at each post-vaccination visit
- Number of visits during which bacteria are detected
- Magnitude of bacterial colonization (number of cfu) per post-vaccination visit
- Cough, spasmodic cough and any symptom from the respiratory tract will be described for colonized and not colonized participants

2) Immunogenicity:

Per dose, group, colonized/not colonized and randomized allocation:

- IgG and IgA antibodies against PT, FHA, PRN, and fimbriae 2/3 in serum at visits 2, 4, 6, 7, 8, 9 and 10
 - Geometric mean levels
 - Number and proportion of participants with positive responses, defined by at least 100% increase from pre- to post-vaccination, to at least 4 times MLD after vaccination

Samples will be tested blindly for *pertussis* specific antibodies in batch for each group. Antibody levels to PT, FHA, PRN, and fimbriae 2/3 will be expressed in IU/mL calibrated against reference antisera from the National Institute for Biological Standards and Controls.

- **Analysis strategy**

The immunogenicity criteria analysis will be performed on the mITT population and based on available data (without missing data handling) with the hypothesis of MCAR.

A robustness analysis will be performed and missing values will be imputed by the median of immunogenicity values in the placebo group.

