3.7. SECONDARY SAFETY ENDPOINT

Per group and randomized allocation:

- at least one episode of cough or spasmodic cough, described by grade, between Day 4 and Day 28
- at least one solicited or unsolicited adverse reaction from respiratory tract between Day 0 and Day 28
- at least one AEFI with difficulties in breathing (asthma, spasmodic cough, pneumonia) between Day 0 and Day 28
- at least one other AEFI from the respiratory tract between Day 0 and Day 28
- at least one episode of cough, described by grade, between Day 0 and Day 28
- at least one episode of spasmodic cough, described by grade, between Day 0 and Day 28
- at least one solicited systemic AEFI between Day 0 and Day 28 (fever, headache, tiredness)
- at least one unsolicited AEFI between Day 0 and Day 28

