3.8. OTHER SECONDARY ENDPOINTS

1) Colonization of the BPZE1 strain in the nasopharyngeal mucosa:

Per dose, group and randomized allocation:

- Number and proportion of participants who have been colonized by the modified *B. pertussis* strain BPZE1 at each time point
- Number of days during which bacteria are detected
- Quantity of bacterial colonization (number of cfu) per post-vaccination visit
- Cough, spasmodic cough and any symptom from the respiratory tract will be described for colonized and not colonized participants

2) Immunogenicity:

Per dose, group, colonized/not colonized and randomized allocation:

- IgG and IgA antibodies against PT, FHA, PRN, and fimbriae 2/3 in serum at visits 2, 4, 6, 7, 8, 9 and 10
 - Geometric mean levels and 95%CI for pre and post vaccination (expressed in IU/mL calibrated against reference antisera from the National Institute for Biological Standards and Controls)

- Participants with positive responses (n, % and 95%CI), defined by at least 100% increase from pre- to post-vaccination, to at least 4 times MLD after vaccination (n, % at each post-vaccination time point)

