3.10. INTERIM REPORTS FOR DSMB

Overall, per group and randomized allocation, and by period (pre/post vaccination):

- Number and proportion of participants with at least :
 - one AEFI during available follow-up
 - one AR during available follow-up
 - one SAE during available follow-up
 - one work accident
- Number of following AEs during available follow-up:
 - Solicited or unsolicited adverse reaction from respiratory tract
 - AEFI with difficulties in breathing (asthma, spasmodic cough, pneumonia)
 - Cough
 - spasmodic cough
 - solicited systemic adverse event
 - unsolicited adverse event

- Participants with at least one cough or spasmodic cough of grade 2 or higher between Day 0 and Day 28 (n, %)
- Participants with at least one other respiratory tract AE related or possibly related to vaccination of grade 3 or higher between Day 0 and Day 28 (n, %)
- Participants with any other AE related or possibly related to vaccination of grade 3 or higher between Day 0 and Day 28 (n, %)
- Participants with at least of the adverse events listed above (primary endpoint) (n, %, 95% CI)
- Participants with at least one solicited or unsolicited adverse reaction from respiratory tract between Day 0 and Day 28 (n, %, 95% CI)
- Participants with at least one AEFI with difficulties in breathing (asthma, spasmodic cough, pneumonia) between Day 0 and Day 28 (n, %, 95% CI)
- Participants with at least one other AEFI from the respiratory tract between Day 0 and Day 28 (n, %, 95% CI)
- Participants with at least one cough between Day 0 and Day 28 (n, %, 95% CI)
 - duration of symptoms (mean, median, SD, IQR, 95% CI)
- Participants with at least one spasmodic cough between Day 0 and Day 28 (n, %, 95% CI)
 - duration of symptoms (mean, median, SD, IQR, 95% CI)
- Participants with at least one solicited systemic adverse events between Day 0 and Day 28 (fever, headache, tiredness) (n, %, 95% CI)
- Participants with at least one unsolicited adverse event between Day 0 and Day 28 (n, %, 95% CI)

Detailed listings of individual events will be provided in an appendix of the reports.

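### The SAP's analysis sections name a respiratory endpoint and a colonization measure that differ from those defined, and a late-SAE endpoint in the synopsis is missing from the protocol body and the SAP

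*Combined protocol and SAP*

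**What the plan says.** **Respiratory endpoint.** SAP 2.1.2 defines it as "at least one solicited or unsolicited AEFI from respiratory tract between Day 0 and Day 28". The synopsis and protocol XIV.2 agree. In SAP 3.7, which specifies the table, the row is "at least one solicited or unsolicited adverse reaction from respiratory tract between Day 0 and Day 28". SAP 3.10 uses the same term for the DSMB report: "Participants with at least one solicited or unsolicited adverse reaction from respiratory tract between Day 0 and Day 28". SAP 3.5.2 and 3.10 also use it for a count of events. Protocol XIII.1 defines the two terms differently. An AEFI is an occurrence that "does not necessarily have a causal relationship with the usage of the vaccine". For reactions it says "AR are all untoward and unintended responses to an IMP related to any dose administered", and it adds that an event qualifies when the investigator or sponsor judges it possibly, probably or definitely related.

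**Colonization.** Protocol XIV.3 and SAP 2.1.3 list "Number of visits during which bacteria are detected", and protocol XV.2.3 repeats visits. SAP 3.8 lists "Number of days during which bacteria are detected" and gives no rule for deriving days.

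**Late SAEs.** The synopsis lists as a secondary safety endpoint "at least one SAE related or possibly related to vaccination declared between D28 and the end of the trial". Protocol XIV.2, SAP 2.1.2 and SAP 3.7 do not contain it. SAP 3.5.2 counts participants with at least one SAE over the whole follow-up.

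**The concern.** Tables are programmed from section 3 of the SAP. If a programmer applies the protocol's definition of an adverse reaction, the overall respiratory row drops every participant whose respiratory events were all judged unrelated. Respiratory tolerability is part of the primary objective, and the same row goes to the DSMB before each dose escalation. A causality opinion would then decide a rate that was defined without one.

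A count of days with bacteria invites reading as duration of carriage, which cultures several days apart cannot fix. For late safety, every other listed secondary safety endpoint stops at Day 28, while the secondary safety objective runs to 6 months in the protocol and to 12 months for groups 1-3 in the SAP.

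**Working it through.** The plan states no figure for these endpoints, so nothing needs reproducing. Its sample-size figures concern the primary endpoint and are not touched. The check sets the texts side by side and then sizes each mismatch.

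**1. AEFI against adverse reaction**

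Does the SAP treat the terms as different? Yes. Its acronym list carries both, and 3.5.2 and 3.10 list participants with at least one AEFI and with at least one AR as separate items. A programmer therefore has grounds to apply the filter.

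Does the filtered row fit its neighbours? SAP 3.7 also has unfiltered rows for breathing-difficulty AEFI and for other respiratory AEFI. Under the definition in 2.1.2 the overall row is the union of those two, so it is at least as large as either. Under the formal AR reading this need not hold.

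To size it, let x be the participants in an arm of n = 12 with any respiratory AEFI, and u the share of them with no respiratory event judged related. The AEFI row is x/n and the AR row is x(1 - u)/n. Intervals are exact binomial, as SAP 2.2.1 specifies. The documents give neither x nor u. Taking x = 9 as an assumption:

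| u | AR row | 95% CI | AEFI row | 95% CI |
|---|---|---|---|---|
| 0 | 9/12 = 75% | 42.8 to 94.5% | 75% | 42.8 to 94.5% |
| 1/3 | 6/12 = 50% | 21.1 to 78.9% | 75% | 42.8 to 94.5% |
| 2/3 | 3/12 = 25% | 5.5 to 57.2% | 75% | 42.8 to 94.5% |

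If none of the 9 had breathing difficulty, the row for other respiratory AEFI would show 75% in every case. In the last line the overall row would then show 25%, below its own subset.

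**2. Days against visits**

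Cultures up to Day 28 are taken at Visits 3 to 8, on nominal Days 4, 7, 11, 14, 21 and 28. Visit 8' is added only if the Day 28 culture is positive. Take a participant positive on Days 7, 11 and 14 only:

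- Positive visits: 3.
- Positive sampling days: 3, the same number.
- Duration, assuming carriage is continuous between positive cultures: at least Days 7 to 14, which is 14 - 7 + 1 = 8 days. At most it runs from the day after the negative Day 4 culture to the day before the negative Day 21 culture, which is 20 - 5 + 1 = 16 days.

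So days either repeats the visit count or is a duration that the data only bracket.

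**3. SAEs after Day 28**

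| Place | Related SAE, Day 28 to end of trial |
|---|---|
| Synopsis | listed |
| Protocol XIV.2 | absent |
| SAP 2.1.2 | absent |
| SAP 3.7 | absent |
| SAP 3.5.2 | any SAE over the whole follow-up, with no Day 28 cut and no restriction to related events |

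The conflict begins between the synopsis and XIV.2. The SAP follows XIV.2.

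**The case against.** The best defence on the first item is that the protocol often uses AR as a plain label for respiratory symptoms. In VI.3.3 subjects enter respiratory ARs in the Diary, in VI.3.4 to VI.3.11 staff interview about them, and XIII.2 groups respiratory adverse reactions with adverse events. Diary entries involve no causality judgement. SAP 3.5.2 and 3.10 place the respiratory line under counts of AEs, apart from the AR item. Where the SAP wants related events in the primary endpoint, it says so. This makes a wording slip plausible. It does not settle the meaning, because the formal definition stands and two competent programmers could produce different tables.

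A reader might infer that respiratory frequency would be hidden from the DSMB. The documents do not support that. Only the overall respiratory lines are affected. The rows for cough, spasmodic cough, breathing difficulty and other respiratory AEFI carry no such filter, and the DSMB also receives listings of individual events.

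On the second item, one culture per visit means that days can be read literally as positive sampling days, which makes it harmless. Nothing in SAP 3.8 says that a duration is meant, so it would go too far to say that the plan will report a made-up duration.

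On the third, a reader might conclude that SAP 3.7 dropped the endpoint, or that the late-safety objective has no result at all. Neither holds. SAP 3.7 agrees with XIV.2 and SAP 2.1.2, and SAP 3.5.2 reports AEFI, AR and SAE over the whole follow-up. Any late related SAE is inside that SAE count.

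**Conclusion.** All three inconsistencies are in the current text and should be corrected.

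- **Respiratory row.** This is the most consequential. On the formal reading of AR, the overall row is restricted to related events. The understatement is zero if every affected participant has a related event and grows with the share judged unrelated. In the assumed example it goes from 75% down to 50% or 25%. On the loose reading nothing changes. The text does not say which reading applies.
- **Colonization.** Days is either a synonym for visits or a quantity that cannot be derived from the schedule. The 8-to-16-day range assumes continuous carriage and nominal visit days.
- **Late SAEs.** The data are collected and counted, but the endpoint named in the synopsis has no table of its own.

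All affected endpoints are secondary and descriptive, with no comparison between arms. The primary endpoint and the sample size are not affected.

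**What to change.** 1. In SAP 3.5.2, 3.7 and 3.10, write AEFI from the respiratory tract, and show events judged possibly, probably or definitely related as a sub-row.
2. In SAP 3.8, restore the number of visits. If duration is wanted, report minimum and maximum bounds from the adjacent negative cultures and state the assumption of continuous carriage.
3. Reconcile the synopsis with protocol XIV.2. Preferably restore the related-SAE endpoint from Day 28 in XIV.2, SAP 2.1.2 and SAP 3.7, and state which visit closes the window, since the SAP follows groups 1-3 to 12 months and group 4 to 6 months. Otherwise remove it from the synopsis and give the reason.

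The cost is wording in the SAP and protocol and a few table rows. No new data are needed. The overall respiratory rate can only stay the same or rise, so it may look less favourable.

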3.8. OTHER SECONDARY ENDPOINTS

1) Colonization of the BPZE1 strain in the nasopharyngeal mucosa:

Per dose, group and randomized allocation:

- Number and proportion of participants who have been colonized by the modified *B. pertussis* strain BPZE1 at each time point
- Number of days during which bacteria are detected
- Quantity of bacterial colonization (number of cfu) per post-vaccination visit
- Cough, spasmodic cough and any symptom from the respiratory tract will be described for colonized and not colonized participants

2) Immunogenicity:

Per dose, group, colonized/not colonized and randomized allocation:

- IgG and IgA antibodies against PT, FHA, PRN, and fimbriae 2/3 in serum at visits 2, 4, 6, 7, 8, 9 and 10
 - Geometric mean levels and 95%CI for pre and post vaccination (expressed in IU/mL calibrated against reference antisera from the National Institute for Biological Standards and Controls)

- Participants with positive responses (n, % and 95%CI), defined by at least 100% increase from pre- to post-vaccination, to at least 4 times MLD after vaccination (n, % at each post-vaccination time point)

